4.3. Exploratory Objectives

The exploratory objectives of this study are as follows:

Objective

Exploratory objectives evaluating the response to baricitinib treatment regimens on other patient reported outcomes may include dichotomous endpoints or change from baseline for the following measures: Patient-Oriented Eczema Measure (POEM), Dermatology Life Quality Index (DLQI), Itch Numerical Rating Scale (NRS), Atopic Dermatitis Sleep Scale (ADSS), Skin Pain NRS, Hospital Anxiety Depression Scale (HADS), Eczema Area and Severity Index score (EASI) and SCORing Atopic Dermatitis (SCORAD). Topical corticosteroids(TCS) use will be explored.
 
 Time to First Eczema Area and Severity Index score (EASI) 75% Reduction Response by Week 16 Time to First Investigator's Global Assessment IGA (0,1) Response by Week 16 Time to First Itch 4 point reduction Response by Week 16 Proportions of patients achieving a Skin pain 4-pt improvement for those with baseline Skin pain ≥ 4 by Week 16 Proportions of patients achieving a DLQI 4-pt improvement for those with baseline DLQI ≥ 4 by Week 16 Proportions of patients achieving a DLQI 5 score or less for those with baseline DLQI > 5 Proportions of patients achieving a DLQI 0 or 1 by Week 16 Proportions of patients achieving a POEM 4-pt improvement for those with baseline POEM ≥ 4 by Week 16 Proportions of patients achieving a HADS Anxiety < 8 for those with baseline HADS A ≥ 8 by Week 16 Proportions of patients achieving a HADS Depression < 8 for those with baseline HADS D ≥ 8 by Week 16 Proportions of patients achieving a HADS A or HADS D < 8 for those with baseline HADS A ≥ 8 or HADS D ≥ 8 by Week 16

Objective

• HADS total score change from baseline using mixed model repeated measures (MMRM) by Week 16• Proportions of patients achieving a ADSS2 1.5-pt improvement for those with baseline ADSS2 ≥ 1.5 by Week 16• Mean change from baseline in the score of Item 1 of the ADSS at 1 week and 16 weeks• Mean change from baseline in the score of Item 3 of the ADSS at 1 week and 16 weeks• Mean change from baseline in EASI score at Week 16• Mean percentage change from baseline in SCORing Atopic Dermatitis (SCORAD) score at Week 16• Proportions of patients achieving a DLQI 5 score or less for those with baseline DLQI > 5 at Weeks 28, 40, 52, 64, 76, 88 and 104• Mean change from baseline in DLQI score at Weeks 28, 40, 52, 64, 76, 88 and 104

[figure not shown]

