6.2.3. Definition of Baseline and Postbaseline Measures

The baseline value for efficacy and health outcomes variables measured at scheduled visits is defined as the last nonmissing measurement on or prior to the date of first study drug administration (expected at Week 0, Visit 2).

The baseline value for the daily diary assessments (Itch NRS, ADSS, Skin Pain NRS, PGI-S-AD) is defined as the mean of the nonmissing assessments in the 7 days prior to the date of first study drug administration.

If there are less than 4 nonmissing assessments in the baseline diary window, the interval lower bound can be extended up to 7 additional days, 1 day at a time, to obtain the 4 most recent nonmissing values. If there are not at least 4 nonmissing assessments in the baseline period, the baseline mean is missing.

Baseline for the safety analyses is defined as the last nonmissing scheduled (planned) measurement on or prior to the date of first study drug administration for continuous measures

by-visit analyses and all nonmissing measurements on or prior to the date of first study drug administration for all other analyses.

Postbaseline

Postbaseline measurements are collected after study drug administration for electronic patient-reported outcome (ePRO), Itch NRS, Skin Pain NRS, ADSS and PGI-S-AD up to Week 16 (Visit 8). Other postbaseline measurements are collected up to Week 104 (Visit 15).

Postbaseline for the safety analyses is defined as the nonmissing scheduled (planned) measurements after the date of first study drug administration for continuous measures by visit analyses and all nonmissing measurements after the date of first study drug administration for all other analyses.

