Nonmissing efficacy data collected at scheduled visits (e.g., = Electronic version of Clinical Outcome Assessment [eCOA], clinician-reported outcome [ClinRO]) will be used for analyses. If an assessment is missing at a scheduled visit, an unscheduled postbaseline assessment can be used provided it falls within a ± 4 day window of the scheduled visit date. If there is more than 1 unscheduled visit within the defined visit window and no scheduled visit assessment is available, the unscheduled visit closest to the scheduled visit date will be used. If 2 unscheduled visits of equal distance are available, then the latter of the 2 will be used. If there is no nonmissing measure collected at the scheduled visit, or an unscheduled visit falling within the visit window, the assessment is missing for that scheduled visit.

For Treatment Period 1, postbaseline daily diary endpoints will be the mean of weekly visit windows (diary windows) anchored on day of first dose (Day 1) for Week 1 to Week 14 as follows:

Week	1	2	3	4	5	6	7	8	9	10	11	12	13	14
Day	1-7	8-14	21	22-28	29-35	36-42	43-49	50-56	57-63	64-70	71-77	78-84	85-91	92-98

Week 16 Daily Diary Window Construction

The following sequential steps will be used to determine the Week 16 diary window. The general goal is to anchor on the scheduled Week 16 visit (or a proximal unscheduled visit) if such a visit exists, or to use an interval based on days in study for cases where a scheduled Week 16 or a proximal surrogate does not exist.

Step 1: If the Week 16 scheduled visit exists, the Week 16 diary interval is the 7 days prior to the Week 16 date provided that window has at least 4 nonmissing observations. If there are less than 4 nonmissing observations, the diary window's lower bound will be extended 1 day at a time (up to day 99) to a maximum of 14 days prior to the Week 16 date until 4 nonmissing observations are obtained. If, after extending this diary window's lower bound to 14 days, there are less than 4 nonmissing observations then go to Step 3.

Step 2: If the Week 16 scheduled visit does not exist, the 7 days prior to the last visit (scheduled or unscheduled) occurring after Day 105 and up to Visit 8 will constitute the Week 16 diary

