6.2.5. Derived Data

The following endpoints are derived from collected data:

- Age (year), derived using first dose date as the reference start date and July 1 of birth year, and truncated to a whole-year (integer) age. Patients whose derived age is less than 18 will have the required minimum age of 18 at informed consent confirmed. Reporting for age, age groups, and lab ranges, however, will be based on their derived age.
- Age group (<65, \geq 65 years old)
- Age group (<65, \geq 65 to <75, \geq 75 to <85, \geq 85 years old)
- Body mass index (BMI) (kg/m²) = Weight (kg)/((Height (cm)/100)²)
- BMI category (<25 kg/m², \geq 25 to <30 kg/m², \geq 30 kg/m²)
- The duration of AD from diagnosis (year) = [(Date of informed consent – Date of AD diagnosis)+1]/ 365.25.

If year of onset is missing, duration of AD will be set as missing. Otherwise, unknown month will be taken as January, and unknown day will be taken as 01. The duration of AD will be rounded to 1 decimal place.

- Duration of AD (years) category (0 to <2 years, \geq 2 to <5 years, \geq 5 to <10 years, \geq 10 to <20 years, \geq 20 years)
- Diagnosis age: (number of months between date of AD diagnosis and July 1 of birth year) / 12, and truncated to a whole-integer age
- Diagnosis age group (<18, \geq 18 and <50, \geq 50 years old)
- Change from baseline = postbaseline measurement at Visit x – baseline measurement. If a baseline value is missing, it will not be imputed and the change from baseline will not be calculated.
- Percent change from baseline at Visit x:

((Postbaseline measurement at Visit x - Baseline measurement)/Baseline measurement)*100.

If a baseline value is missing, it will not be imputed and percent change from baseline will not be calculated.

- Weight (kg) = weight (lbs) * 0.454.
- Weight category (<60 kg, \geq 60 to <100 kg, \geq 100 kg)
- Height (cm) = height (in) * 2.54.
- Cyclosporine inadequate efficacy response(yes, no)
 - Set yes if the reason for discontinuation is inadequate response
- Cyclosporine intolerance (yes, no)
 - Set yes if the reasons for discontinuation are: intolerance to medication or contraindication (physician indicated cyclosporine was used and a contraindication was noted)
- Cyclosporine contraindication [ineligible] (yes, no)
 - Set to yes if cyclosporine never used because of a contraindication
- Cyclosporine inadvisable (yes, no)

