Itch Numeric Rating Scale (NRS)	
The Itch NRS is a patient-administered, 11-point horizontal scale anchored at 0 and 10, with 0 representing “no itch” and 10 representing “worst itch imaginable.” Overall severity of a patient’s itching is indicated by selecting the number that best describes the worst level of itching in the past 24 hours (Naegeli et al. 2015; Kimball et al. 2016). Refer to Section 6.2.3 for details on how to calculate the weekly score which will be used in the continuous analysis.
	
Itch NRS score
 
 ▪ Change from baseline in Itch NRS ▪ Percent change from baseline in Itch NRS ▪ 4-point itch improvement in subgroup of patients with baseline Itch NRS ≥ 4 ▪ Cumulative Incidence Function of Time to reaching Itch NRS 4-pt improvement (primary censoring rule) 	
Single item; range 0-10. Refer to Section 6.2.3 on how to derive the visit score.
 
Change from baseline: observed itch score – baseline itch score % change from baseline: $100 \times \frac{\text{Observed score} - \text{Baseline}}{\text{Baseline}}$
 
Change from baseline ≤ 4 and baseline ≥ 4
 
first time reaching Itch NRS 4-pt improvement as event 1, rescue and discontinue for lack of efficacy as event 2, censor up to week 16
	
Refer to Section 6.2.3 on how to derive the visit score.
 
Missing if baseline or observed value is missing
 
Missing if baseline is missing or < 4 or observed value is missing
 
Use observed value, rescue and discontinue for lack of efficacy as competing event, censor up to week 16

Description and Derivation of Health Outcomes and Quality-of-Life Measures

Measure	Description	Variable	Derivation/Comment	Imputation Approach if with Missing Components
Skin Pain NRS	The Skin Pain NRS is a patient-administered, 11-point horizontal scale anchored at 0 and 10, with 0 representing “no pain” and 10 representing “worst pain imaginable.” Overall severity of a patient’s skin pain is indicated by selecting the number that best describes the worst level of skin pain in the past 24 hours. Refer to Section 6.2.3 for details on how to calculate the weekly score which will be used in the continuous analysis.	Skin Pain NRS score	Single item; range 0- 10. Refer to Section 6.2.3 on how to derive the visit score.	Refer to Section 6.2.3 on how to derive the visit score.

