		▪ Change from baseline in Skin Pain NRS	Change from baseline: observed skin pain score – baseline skin pain score	Missing if baseline or observed value is missing
		▪ 4-point Skin Pain improvement in subgroup of patients with baseline Skin Pain NRS ≥ 4	Change from baseline ≤ -4 and baseline ≥ 4	Missing if baseline is missing or < 4 or observed value is missing

Description and Derivation of Health Outcomes and Quality-of-Life Measures

Measure	Description	Variable	Derivation/Comment	Imputation Approach if with Missing Components
Atopic Dermatitis Sleep Scale (ADSS)	
The ADSS is a 3-item, patient-administered questionnaire developed to assess the impact of itch on sleep including difficulty falling asleep, frequency of waking, and difficulty getting back to sleep last night. Patient's rate their difficulty falling asleep and difficulty getting back to sleep, items 1 and 3, respectively, using a 5-point Likert-type scale with response options ranging from 0 "not at all" to 4 "very difficult." Patients report their frequency of waking last night, item 2, by selecting the number of times they woke up each night, ranging from 0 to 29 times. The ADSS is designed to be completed each day with respondents thinking about sleep "last night." Each item is scored individually. Refer to Section 6.2.3 for details on how to calculate the weekly score which will be used in the continuous analysis.
	
 ▪ Item 1 score of ADSS ▪ Item 2 score of ADSS ▪ Item 3 score of ADSS ▪ Change from baseline in score of Item 1 of ADSS ▪ Change from baseline in score of Item 2 of ADSS ▪ Change from baseline in score of Item 3 of ADSS ▪ 1.5 point improvement on Item 2 of ADSS 	
Single items: Item 1, range 0 to 4; Item 2, range 0 to 29; Item 3, range 0 to 4. Refer to Section 6.2.3 on how to derive the visit score.
 
Change from baseline: observed ADSS item score – baseline ADSS item score
 
Change from baseline ≤ -1.5 and baseline ≥ 1.5 in score of Item 2 of ADSS
	
Refer to Section 6.2.3 on how to derive the visit score.
 
Missing if baseline or observed value is missing.
 
Missing if baseline is missing or < 1.5 or observed value is missing.

Description and Derivation of Health Outcomes and Quality-of-Life Measures

Measure	Description	Variable	Derivation/Comment	Imputation Approach if with Missing Components

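### The key secondary itch responder rule in SAP Table JAIW.6.6 lacks its minus sign, and two change formulas in the same table use the wrong term

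*SAP*

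**What the plan says.** - **Itch rule.** SAP Section 6.12, Table JAIW.6.6, Itch NRS row: "Change from baseline ≤ 4 and baseline ≥ 4". The variable is labelled as a 4-point itch improvement among patients with baseline of at least 4.
- **Sign convention.** Section 6.2.5: "Change from baseline = postbaseline measurement at Visit x – baseline measurement". The itch row repeats this as observed minus baseline, and describes a 0 to 10 scale on which 10 is the worst itch.
- **Intended direction.** Section 4.3 lists "Time to First Itch 4 point reduction Response by Week 16". Sections 4.2.1 and 6.6 speak of a 4-point improvement.
- **Sister rows.** For Skin Pain: "Change from baseline ≤ -4 and baseline ≥ 4". POEM and DLQI use the same cut-off. For ADSS Item 2: "Change from baseline ≤ -1.5 and baseline ≥ 1.5 in score of Item 2 of ADSS".
- **Scale of the scores.** Section 6.2.3: the diary baseline "is defined as the mean of the nonmissing assessments in the 7 days prior to the date of first study drug administration", and "postbaseline daily diary endpoints will be the mean of weekly visit windows". Itch scores are therefore means and not only whole numbers.
- **Other formulas.** In Table JAIW.6.6, the change in presenteeism is observed presenteeism minus baseline absenteeism, and the change in HADS total is an observed domain score minus the baseline total. In Table JAIW.6.4, the IGA responder rule asks for a score of 0 or 1 and a change of at most 2, again without a minus sign.

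**The concern.** The itch row is the only place where the SAP turns the 4-point itch improvement into a formula, and that formula contradicts the row's own label. The derived variable is a key secondary endpoint at Weeks 1, 2, 4 and 16 for both doses. It also feeds the placebo multiple imputation (Section 6.4.5), the tipping-point analysis (6.4.6), the subgroup analyses (6.15) and the time to itch response (6.2.4).

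If the rule were programmed as written, almost any patient with a usable score would be a responder, including patients whose itch had not improved or had worsened. Section 6.4.1 imputes missing scores as non-response, so the endpoint would mostly record who still had an uncensored score and would say little about itch.

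The presenteeism and HADS formulas matter less. HADS total is exploratory, and presenteeism is an other secondary measure outside multiplicity control. Both are still stated rules for planned analyses.

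**Working it through.** The SAP attaches no figure to these rules, so there is none to reproduce. The check compares the passages and counts which scores each rule accepts.

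**1. Direction.** Let b be baseline itch and s the later score, both on 0 to 10 with 10 worst. Change is s - b. A 4-point improvement means s ≤ b - 4, that is, s - b ≤ -4.

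**2. Rows side by side.**

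| Measure | Cut-off on change, as written |
|---|---|
| Skin Pain NRS | ≤ -4 |
| POEM | ≤ -4 |
| DLQI | ≤ -4 |
| ADSS Item 2 | ≤ -1.5 |
| SCORAD75 / SCORAD90 (percent change) | ≤ -75 / ≤ -90 |
| **Itch NRS** | **≤ 4** |
| **IGA (0,1)** | **≤ 2** |

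**3. Reach of the literal itch rule, continuous scores.** With b from 4 to 10 and s from 0 to 10, the area of possible scores is 6 × 10 = 60.
- s - b > 4 is possible only for b below 6. That area is the integral of (6 - b) from 4 to 6, which is 2. The literal rule covers (60 - 2)/60 = 58/60 = 96.7%.
- s - b ≤ -4: the integral of (b - 4) from 4 to 10 is 18, so the intended rule covers 18/60 = 30%.
- Unchanged or worse (s ≥ b): the integral of (10 - b) from 4 to 10 is 18. The literal rule accepts 18 - 2 = 16 of it, 16/18 = 89%. The intended rule accepts none.
- For b ≥ 6 the largest possible change is 10 - 6 = +4, so every score passes the literal rule.

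**4. Cross-check on whole-number scores.** There are 7 × 11 = 77 pairs (b, s). The literal rule accepts 74; only (4,9), (4,10) and (5,10) fail. It accepts 25 of the 28 unchanged or worse pairs. The intended rule accepts 28 of 77, none of them unchanged or worse.

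**5. Hypotheses affected.** Section 6.6 lists 12 endpoints for each of two doses, 24 in all. Itch response is endpoints 3, 5, 7 and 8, so 4 × 2 = 8 of 24.

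**6. Presenteeism.** Let P be observed presenteeism, and P0 and A0 baseline presenteeism and absenteeism. The error is (P - A0) - (P - P0) = P0 - A0. Each lies between 0 and 100, so the error can run from -100 to +100 percentage points. Illustration with assumed values: presenteeism unchanged at 50% and baseline absenteeism 10% gives 50 - 10 = +40 instead of 0. The error depends only on baseline values, so randomisation makes its expectation equal across arms. Within-arm changes would be wrong, but the treatment difference would not be biased in expectation.

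**7. HADS total.** Let O be the observed score of one domain, B its baseline, and B2 the baseline of the other domain. Then O - (B + B2) = (O - B) - B2. A patient with no change scores -B2, anywhere from 0 to -21, instead of 0. Illustration with assumed values: 10 on both domains at both visits gives 10 - 20 = -10. The comparison would concern one domain, which the SAP does not name, and not the total.

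**8. IGA.** The randomisation strata are baseline IGA 3 and 4. Reaching 0 or 1 gives changes of -3, -2, -4 or -3. All are -2 or lower, so the missing sign changes nothing here.

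**The case against.** The strongest objection is that the itch item rests on one absent character, which may have been lost when the PDF was converted to text. Other text is visibly missing: the Week 3 diary window in Section 6.2.3 shows only day 21, and in Table JAIW.6.4 the EASI50/75/90 rules and the BSA formula do not appear. The itch and IGA rules both sit in cells that merge several rules. This stands as a possibility. It is not established, because the ADSS and SCORAD cells are merged too and keep their signs. It cannot explain the presenteeism and HADS errors, which are wrong words.

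Second, the row label, the objectives and the definition of change together leave only one sensible reading, so the endpoint is not truly ambiguous. That is right, and a careful programmer would probably have followed the label. The formula is nonetheless the stated derivation, and programs are validated against it.

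Third, the impact is hypothetical and little remains to be affected. Nothing in the SAP shows that a program used the literal rule. The Week 16 lock has been executed, and Section 6.2.3 has "Itch NRS, Skin Pain NRS, ADSS and PGI-S-AD up to Week 16 (Visit 8") as the end of diary collection. Table JAIW.6.7 has no final-lock row for itch, HADS or WPAI. All of this stands, and it limits the remedy to a correction and a check. It does not remove the point, since Section 6.2.1 keeps the Week 16 lock within the scope of this SAP.

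**Conclusion.** The point holds: as written, the itch rule is wrong, and it should be corrected. Taken literally, it would accept 97% of the possible scores in place of 30%, and every score from baseline 6 upward, for 8 of the 24 controlled hypotheses. Those percentages describe the range of possible scores and do not predict response rates.

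The presenteeism and HADS formulas are also wrong, with lower weight. The IGA rule has the same form but no consequence.

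Confidence is medium. The conclusion on itch and IGA assumes that the source SAP lacks the minus sign as the extracted text does; the other two errors do not depend on this. No error in any reported result is shown, and the final-lock analyses are not affected.

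**What to change.** First confirm the itch and IGA wording in the source SAP. Then correct:

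- Table JAIW.6.6, Itch NRS: change of -4 or lower, with baseline of at least 4.
- Table JAIW.6.6, WPAI-AD: observed presenteeism minus baseline presenteeism.
- Table JAIW.6.6, HADS total: observed total minus baseline total.
- Table JAIW.6.4, IGA: change of -2 or lower, for consistency.

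Next, check the Week 16 derivation programs against the corrected text and record the result. Re-run only the outputs that used a literal rule.

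The cost is up to four line edits and one program check; a re-run is needed only if the check finds a literal rule in use.

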6.2.1. Reporting Periods

This study will have data locks as described below.

- An unblinded interim lock was executed after all patients have completed the Week 16 visit (Visit 8) or discontinued. As the primary endpoint (Section 4.2.1) and several secondary endpoints (Section 4.2.2) including safety are evaluated at Week 16, a CSR will report these data.

- An unblinded lock occurred to support the 4-Month Safety Update Report. Additional safety locks to support global submissions may also be performed. Clinical study reports will not be developed based on these safety locks.
- There will be several unblinded locks in support of a Data Monitoring Committee (DMC). Additionally, there will be several blinded locks in support of trial level safety reviews and the Periodic Safety Update Report.
- A final lock will be performed after all patients have completed the Post-Treatment Follow-up Visit (Week 108, Visit 801), discontinued permanently, or entered or switched to Study JAIX. An abbreviated CSR will be developed based on this lock.

The scope of this SAP will be to support the Week 16 unblinding interim lock, 4-Month Safety Update database lock, and the final lock.

The Blinding/Unblinding Plan for Study JAIW will outline efforts to ensure the blinding integrity after unblinded transfers.

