6.3. Adjustments for Covariates

The randomization to treatment groups at Week 0 (Visit 2) is stratified by disease severity (IGA) as described in Section 5.1. Unless otherwise specified, the statistical analysis models will control for disease severity. The covariates used in the logistic model for categorical data will include the parameter value at baseline. The covariates used in the ANCOVA models for continuous data generally will include the parameter's value at baseline. Inclusion of baseline in the ANCOVA models ensures treatment LSMS are estimated at the same baseline value. When an MMRM analysis is performed, baseline value and baseline-by-visit interactions will be included as covariates.

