Hospital Anxiety Depression Scale (HADS)	
The HADS is a 14-item self-assessment scale that determines the levels of anxiety and depression that a patient is experiencing over the past week. The HADS utilizes a 4-point Likert scale (eg, 0 to 3) for each question and is intended for ages 12 to 65 years (Zigmond and Snaith 1983; White et al. 1999). Scores for each domain (anxiety and depression) can range from 0 to 21, with higher scores indicating greater anxiety or depression (Zigmond and Snaith 1983; Snaith 2003).
	HADS score for anxiety and depression domains	Anxiety domain score is sum of the seven anxiety questions, range 0 to 21. Depression domain score is sum of the seven depression questions, range 0 to 21.	N/A – partial assessments cannot be saved.
		Change from baseline in HADS domain	Change from baseline: observed HADS domain score – baseline HADS domain score	Missing if baseline or observed value is missing.
		Change from baseline in HADS total	Change from baseline: observed HADS domain score – baseline HADS total score	Missing if baseline or observed value is missing.
		
 ▪ HADS Anxiety <8 in subgroup of patients with baseline HADS Anxiety score ≥ 8 ▪ HADS Depression <8 in subgroup of patients with baseline HADS Depression score ≥ 8 	observed HADS postbaseline <8 and baseline score ≥ 8 for each HADS domain score	Missing if baseline is missing or <8 or observed value is missing.

Description and Derivation of Health Outcomes and Quality-of-Life Measures

Measure	Description	Variable	Derivation/Comment	Imputation Approach if with Missing Components
Hospital Anxiety Depression Scale (HADS)	The HADS is a 14-item self-assessment scale that determines the levels of anxiety and depression that a patient is experiencing over the past week. The HADS utilizes a 4 point Likert scale (eg, 0 to 3) for each question and is intended for ages 12 to 65 years (Zigmond and Snaith 1983; White et al. 1999). Scores for each domain (anxiety and depression) can range from 0 to 21, with higher scores indicating greater anxiety or depression (Zigmond and Snaith 1983; Snaith 2003).	
 ▪ HADS Anxiety or Depression score <8 in subgroup of patients with baseline HADS Anxiety or Depression score ≥ 8 	observed HADS postbaseline <8 and baseline score ≥ 8 for any HADS domain score	Missing if baseline is missing or <8 or observed value is missing for both domain

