Description and Derivation of Health Outcomes and Quality-of-Life Measures

Measure	Description	Variable	Derivation / Comment	Imputation Approach if with Missing Components
Dermatology Life Quality Index (DLQI)	The DLQI is a simple, patient-administered, 10-item, validated, quality-of-life questionnaire that covers 6 domains including symptoms and feelings, daily activities, leisure, work and school, personal relationships, and treatment. The recall period of this scale is over the “last week.” Response categories include “a little,” “a lot,” and “very much,” with corresponding scores of 1, 2, and 3, respectively, and “not at all,” or unanswered (“not relevant”) responses scored as 0. Scores range from 0-30 with higher scores indicating greater impairment of quality of life. A DLQI total score of 0 to 1 is considered as having no effect on a patient’s health-related QoL (Hongbo et al. 2005), and a 4-point change from baseline is considered as the minimal clinically important difference threshold (Khilji et al. 2002; Basra et al. 2015).	Symptoms and feelings domain	Sum of Questions 1 and 2, range 0 to 6.	N/A – partial assessments cannot be saved.
		Daily activities domain	Sum of Questions 3 and 4, range 0 to 6.	N/A – partial assessments cannot be saved.
		Leisure domain	Sum of Questions 5 and 6, range 0 to 6.	N/A – partial assessments cannot be saved.
		Work and school domain	Sum of Questions 7 and 7B (if answered), range 0 to 3. Responses of “yes” and “no” on Question 7 are given scores of 3 and 0 respectively. If Question 7 is answered “no” then Question 7b is answered with “a lot”, “a little”, “not at all” getting scores of 2, 1, 0 respectively.	N/A – partial assessments cannot be saved.
		Personal relationships domain	Sum of Questions 8 and 9, range 0 to 6.	N/A – partial assessments cannot be saved.
		Treatment domain	Question 10, range 0 to 3.	N/A – partial assessments cannot be saved.
		DLQI total score	DLQI total score: sum of all 6 DLQI domain scores, range 0 to 30.	N/A – partial assessments cannot be saved.
		Change from baseline in DLQI	Change from baseline: observed DLQI score – baseline DLQI score	Missing if baseline or observed value is missing.

Description and Derivation of Health Outcomes and Quality-of-Life Measures

Measure	Description	Variable	Derivation / Comment	Imputation Approach if with Missing Components

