		Percentage of absenteeism	Percent work time missed due to problem: $(Q2/(Q2 + Q4)) * 100$	If Q2 or Q4 is missing, then missing.
		Change from baseline in absenteeism	Change from baseline: observed absenteeism – baseline absenteeism	Missing if baseline or observed value is missing.
		Percentage of presenteeism	Percent impairment (reduced productivity while at work) while working due to problem: $(Q5/10) * 100$	If Q5 is missing, then missing.
		Change from baseline in presenteeism	Change from baseline: observed presenteeism – baseline absenteeism	Missing if baseline or observed value is missing.
		Overall work impairment	Percent overall work impairment (combines absenteeism and presenteeism) due to problem: $(Q2/(Q2+Q4) + [(1 - Q2/(Q2+Q4)) * (Q5/10)]) * 100$	If Q2, Q4, or Q5 is missing, then missing.
		Change from baseline in work impairment	Change from baseline: observed work impairment – baseline work impairment	Missing if baseline or observed value is missing.

Description and Derivation of Health Outcomes and Quality-of-Life Measures

Measure	Description	Variable	Derivation/Comment	Imputation Approach if with Missing Components
Work Productivity and Activity Impairment: Atopic Dermatitis (WPAI-AD)	
The WPAI-AD records impairment due to AD during the past 7 days. The WPAI-AD consists of 6 items grouped into 4 domains: absenteeism (work time missed), presenteeism (impairment at work/reduced on-the-job effectiveness), work productivity loss (overall work impairment/absenteeism plus presenteeism), and activity impairment. Scores are calculated as impairment percentages (Reilly et al. 1993), with higher scores indicating greater impairment and less productivity.
	
Percentage of impairment in activities
 
Change from baseline in impairment in activities
	
Percent activity impairment (performed outside of work) due to problem: $(Q6/10)*100$
 
Change from baseline: observed impairment in activities – baseline impairment in activities
	
If Q6 is missing, then missing.
 
Missing if baseline or observed value is missing.

Description and Derivation of Health Outcomes and Quality-of-Life Measures

Measure	Description	Variable	Derivation / Comment	Imputation Approach if with Missing Components

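### Two change scores in SAP Table JAIW.6.6 subtract the wrong quantity (WPAI-AD presenteeism and HADS total), and the HADS total is never defined

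*SAP*

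**What the plan says.** SAP Section 6.2.5 gives one rule for all change scores: "Change from baseline = postbaseline measurement at Visit x – baseline measurement". Table JAIW.6.6 in Section 6.12 then restates the derivation for each health outcome measure.

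- **WPAI-AD.** Presenteeism is built from Q5 and absenteeism from Q2 and Q4. The row for change in presenteeism reads "observed presenteeism – baseline absenteeism". The rows for absenteeism, overall work impairment and activity impairment each use the same score on both sides.
- **HADS.** The table defines an anxiety and a depression domain score, each from 0 to 21. The row for domain change reads "observed HADS domain score – baseline HADS domain score". The row for total change, directly below it, reads "observed HADS domain score – baseline HADS total score". No row defines a HADS total. For the DLQI the same table does give such a definition: "DLQI total score: sum of all 6 DLQI domain scores, range 0 to 30".

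Both scores are analysed. WPAI-AD change at Week 16 is an other secondary objective without multiplicity adjustment (Section 4.2.2). Table JAIW.6.7 compares presenteeism change with placebo by MMRM, with ANCOVA on mLOCF data as sensitivity analysis. Section 4.3 lists as exploratory "HADS total score change from baseline using mixed model repeated measures (MMRM) by Week 16".

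**The concern.** Table JAIW.6.6 is where a programmer looks for the derivation of these scores. Its cells are more specific than Section 6.2.5, and the SAP does not say which prevails when they differ.

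The presenteeism cell takes the difference of two different quantities: impairment while working, and work time missed. The HADS cell subtracts a two-domain baseline from a one-domain follow-up score and leaves open which domain. Neither result is a change from baseline.

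If the cells were coded literally, the descriptive changes within each arm would be wrong for both scores, and the HADS total comparison would no longer concern the total. A reader who checks outputs against the SAP would find either wrong results or outputs that do not match the written rule.

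**Working it through.** The SAP states no figure for either score, so there is none to reproduce. The check applies each cell as written and then the Section 6.2.5 rule. All patient and arm values below are assumed.

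**Presenteeism.** Let P be presenteeism, (Q5/10) × 100, and A absenteeism, Q2/(Q2 + Q4) × 100. Subscripts 0 and 1 mark baseline and follow-up.

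- As written: P1 − A0. Section 6.2.5: P1 − P0.
- Error: (P1 − A0) − (P1 − P0) = P0 − A0.
- Unchanged patient with Q2 = 4, Q4 = 36, Q5 = 5: A0 = 4/40 × 100 = 10 and P0 = P1 = 50. As written 50 − 10 = +40; correct 50 − 50 = 0.
- Arm means falling from 35 to 25: the correct change is −10. As written:

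| Mean baseline absenteeism | Change as written | Error |
|---|---|---|
| 0% | +25 | +35 |
| 5% | +20 | +30 |
| 10% | +15 | +25 |
| 20% | +5 | +15 |

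For mean baseline presenteeism of 20 to 50% and mean absenteeism of 0 to 20%, the error runs from 20 − 20 = 0 to 50 − 0 = +50 points.

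**Presenteeism contrast.** The error contains baseline quantities only. Randomisation gives these the same expectation in each arm, so the comparison with placebo stays about unbiased.

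For precision, Section 6.3 says "When an MMRM analysis is performed, baseline value and baseline-by-visit interactions will be included as covariates". Take own-baseline presenteeism as that covariate and approximate by a single-visit ANCOVA. Let r = corr(P1, P0), ρ = corr(P0, A0), c = corr(P1, A0), with SD of P = 25 at both visits and SD of A0 = s. The variance of the contrast as written, divided by the correct variance, is

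1 + [s²(1 − ρ²) − 2 × 25 × s × (c − rρ)] / [625(1 − r²)].

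- If c = rρ, meaning baseline absenteeism tells nothing more about later presenteeism once P0 is known, the ratio exceeds 1. Over s = 10 to 20, r = 0.3 to 0.7 and ρ = 0.2 to 0.5 it runs from 1 + 75/568.75 = 1.132 to 1 + 384/318.75 = 2.205. In SE terms this is 1.06 to 1.49.
- If c is free, the direction is not fixed. With s = 10 and r = ρ = 0.5, the denominator is 468.75 and s²(1 − ρ²) = 75. At c = 0.40 the last term is 500 × 0.15 = 75 and the ratio is 1. At c = 0.45 it is 500 × 0.20 = 100, and the ratio is (468.75 + 75 − 100)/468.75 = 0.947, an SE ratio of 0.97.

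**HADS total.** Let A and D now be the anxiety and depression scores, and take the total as A + D. The SAP does not state this sum.

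- With A as the observed domain: A1 − (A0 + D0). Correct: (A1 + D1) − (A0 + D0). Error: −D1.
- With D as the observed domain the error is −A1.

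| A0, D0 → A1, D1 | Correct | As written, A used | As written, D used |
|---|---|---|---|
| 7, 5 → 7, 5 | 0 | −5 | −7 |
| 7, 5 → 5, 3 | −4 | −7 | −9 |
| 7, 5 → 7, 0 | −5 | −5 | −12 |

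The baseline total is balanced in expectation, so the contrast as written is the effect on whichever domain was used. A true effect of −1 on each domain (−2 on the total) would appear as −1. An effect of −2 on anxiety and 0 on depression would appear as −2 or as 0.

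**Reach.** Table JAIW.6.7 gives both scores only ITT analyses up to Week 16 and no Week 16 Responders row. Section 6.2.1 says of that lock: "An unblinded interim lock was executed after all patients have completed the Week 16 visit (Visit 8) or discontinued".

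**The case against.** The best reply is that the SAP shows its own intent. The row labels name the change in presenteeism and in HADS total, Section 6.2.5 gives the general rule, and the neighbouring rows follow it. The HADS cell cannot even be programmed without choosing a domain, which would prompt a query. A 14-item scale with two seven-item domains has an obvious total. All of this stands, and it makes literal programming less likely. It does not make the two cells right, and the sum for the HADS total remains an inference.

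Some stronger readings are tempting, but the document does not support them:

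- *The Week 16 results are wrong.* Code and outputs are not shown, and nothing indicates that the cells were followed literally.
- *The presenteeism comparison is biased.* The error is a baseline quantity, so it is not, apart from chance imbalance and missing records.
- *Precision is necessarily lost.* That holds if c = rρ, but not in general, as the ratio of 0.947 shows.
- *A presenteeism change becomes computable when only baseline Q5 is missing.* The row and Section 6.2.5 both treat change as missing if the baseline is missing, and the natural baseline for this variable is presenteeism. A model with that baseline as covariate would omit the record anyway.

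**Conclusion.** The concern holds as a low-impact correction. Both cells are wrong as written and contradict Section 6.2.5, and the HADS total lacks a definition.

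The consequences depend on literal programming, which the SAP neither shows nor rules out. In that case:

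- The within-arm presenteeism change is uninterpretable and can have the wrong sign. The error is 0 to +50 points over the assumed range. The randomised contrast stays about unbiased, with precision that could move either way.
- The HADS total change is off by minus the omitted domain's postbaseline score, and its contrast describes a single domain.

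One unadjusted other secondary score and one exploratory score are touched, both only up to Week 16. No primary or key secondary result depends on either, and no analysis still planned in the SAP changes. All numerical examples rest on assumed values, and those for HADS also on the total being the sum of the two domains.

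**What to change.** In Table JAIW.6.6:

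1. Change in presenteeism = observed presenteeism minus baseline presenteeism.
2. Add a row: HADS total = anxiety score + depression score (range 0 to 42).
3. Change in HADS total = observed HADS total minus baseline HADS total.

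Then confirm that the Week 16 outputs for these two scores were derived this way, and correct any that were not. The check is still worthwhile after the lock, because Section 6.2.1 keeps the Week 16 lock within the scope of this SAP and has its results reported in a CSR.

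The cost is two edited cells, one added definition and a check of the derivation code and outputs for two scores. No new data are needed.
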